The user may stop the stimulation at any point by pressing the power button and turning the device off or when using the foot pads by lifting one foot from off the device to break the circuit.

The device is recommended to be used for 30 minutes per treatment session with a maximum total treatment time of 3 hours per day as required to minimise the potential for muscle fatigue.

Revitive IX is intended for use in the home setting without the need for involvement of a clinical professional and can be used for up to 3 hours daily in 30 minute sessions.

The retail cost of the device is approximately £160.

The Revitive IX devices have been designed for use with home users in mind and so have been designed to provide simple operation with minimal instruction and without the need for involvement or supervision by a health care professional. The range of capabilities for typical home users can vary by a large degree and so it is highly desirable for the devices to be relatively simple and physically easy to use.

Imperial Clinical Trials Unit	NESIC Clinical Study Protocol V6.0 24/03/2020	Form Number CR001A-T
-------------------------------	---	-------------------------

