## 5.6 Follow-up

Follow-up data will be collected at 3 months, 6 months and 12 months. These visits should be performed at the study site to allow the treadmill test, ABPI / Peripheral

C001A-T v4.0 Effective 5th April 2017

Imperial Clinical Trials Unit	NESIC Clinical Study Protocol V6.0 24/03/2020	Form Number CR001A-T
-------------------------------	---	-------------------------

pulse, haemodynamic assessments to take place, however, in the event that the participant is unable to attend in clinic or the site is unable to accommodate the on-site visit these visits may take place remotely (i.e. over the telephone completely or in combination with postal questionnaires). These visits should only take place remotely if this has been previously discussed and agreed with the Trial Coordinating Centre. Missed assessments as a result of a remote visit should be re-scheduled at a later date as a separate on-site visit, where possible.

Sites should clearly document the mode of follow-up that takes place, such as face to face or over the [contact] Month Visit (end of treatment phase)**

Assessments and data collection will be collected as follows:

- **Treadmill test as per baseline**
- **ABPI / Peripheral pulse as per baseline**
- **Drug history review**
- **Safety reporting**
- **Quality of Life questionnaires as per baseline**
- **Haemodynamic assessment as per baseline**
  - **Duplex ultrasonography:**
    - **In the control group:** only resting values will be undertaken over a 3-minute period.
    - **The intervention group** will have these parameters measured at rest, at 15 and 30-minutes into device use and then at 1 and 5 minutes after device cessation.
  - **Laser Doppler flowmetry:**
    - **In the control group:** this will be at rest for a 3 -minute duration
    - **The intervention group:** data will be collected at rest until 5 minutes after device cessation.
- **Compliance and resource diaries**

Imperial Clinical Trials Unit	NESIC Clinical Study Protocol V6.0 24/03/2020	Form Number CR001A-T
-------------------------------	---	-------------------------

- 1) Exercise compliance** - Participants will be given a compliance diary to complete attendances at the SET (if SET centre), and record the type and frequency of exercise undertaken in their own time during the study period.
- 2) Resource diary** - Participants will be given a resource diary to complete health care resource use during the study period.

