- 3) Device compliance & experience (device arm only)** - Participants randomised to use the NMES device will be provided with a compliance diary to record device use details. In addition, information from the data logger (if applicable) will be assessed in order to cross reference with the compliance diary. At 3 months, a simple device use questionnaire will be taken to report ease of device use and suggest any developments.

Patients will receive weekly text messages during the treatment phase to remind them to complete their diaries, and attend SET or follow exercise advice.

In the event that the participant is unable to attend in clinic or the site is unable to accommodate the on-site visit, this visit may take place remotely (i.e. over the telephone completely or in combination with postal questionnaires). This visit should only take place remotely if this has been previously discussed and agreed with the Trial Coordinating Centre. Missed assessments as a result of a remote visit should be re-scheduled at a later date as a separate on-site visit, where possible.

Sites should clearly document the mode of follow-up that takes place, such as face to face or over the [contact] Month Visit

Assessments and data collection will be collected as follows:

Imperial Clinical Trials Unit	NESIC Clinical Study Protocol V6.0 24/03/2020	Form Number CR001A-T
-------------------------------	---	-------------------------

- **Treadmill test as per baseline**
  - **ABPI / Peripheral pulse as per baseline**
  - **Drug history review**
  - **Safety reporting**
  - **Quality of Life questionnaires as per baseline**
  - **Haemodynamic assessment**
    - **Laser Doppler flowmetry only (no duplex)**: this will be at rest for a 3-minute duration in the most affected leg.
  - **Compliance and resource diaries**
1. **Exercise compliance** - Participants will be given a compliance diary to complete attendances at the SET if it runs past the 3-month visit (if SET centre), and record the type and frequency of exercise undertaken in their own time during the study period.
  2. **Resource diary** - Participants will be given a resource diary to complete health care resource use during the study period.

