### **8.3 Statistical analysis**

The primary analysis will estimate the mean difference in AWD between the two intervention arms using a linear regression model which will include intervention arm, baseline AWD, and the randomisation stratification variable 'centre' as covariates. A repeated measure analysis will be undertaken, including patient as a random effect, to investigate the relationship between AWD and independent

Imperial Clinical Trials Unit	NESIC Clinical Study Protocol V6.0 24/03/2020	Form Number CR001A-T
-------------------------------	---	-------------------------

baseline variables such as body mass index (BMI) with the model including adjustment for centre and baseline AWD. Multiple imputation will be undertaken for all participants who are missing values or drop out by three months. Causal inference methods will be used to estimate treatment effects that account for compliance with the allocated intervention (NMES, SET, EA). Where necessary, data will be transformed to meet normality assumptions. All statistical tests will be two-tailed with a 5% significance level.

Patient characteristics will be summarised. Summaries of continuous variables will be presented as means and standard deviations if normally distributed, and as medians and inter-quartile ranges for skewed data; categorical variables will be presented as frequencies and percentages. Data on the socioeconomic status of patients will be summarised by centre.

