#### Summary scores

- Physical components score (PCS)
- Mental component score (MCS)

Imperial Clinical Trials Unit	STATISTICAL ANALYSIS PLAN	NESIC
-------------------------------	---------------------------	-------

- **Compliance Classification**

We have classified a participant as “compliant” if they have done at least 75% of the recommended target minutes for Device use, at least 75% of the recommended EA minutes performing exercises and attend at least 50% of SET sessions by the end of the treatment period. Then compliance can be dichotomised, coding “Yes, complied” if the patient complied with the recommended threshold treatment and “No” if patient did not comply. This classification is obtained by combining the compliance classification of the three instruments used to collect compliance information from each intervention (Device, SET and EA). Procedures for these classifications are outlined in Appendix 3 section 13.3).

For each treatment group, a patient is considered compliant if they are compliant for all of their assigned treatments. Therefore, for each of the treatment groups compliance is defined as follows:

- EA: compliant if done 75% or more of recommended level of EA (75% of minutes performing exercises recommended by centre)
- EA + SET: compliant if done 75% or more of recommended level of EA and attended 50% or more SET sessions held by centre.
- EA + NMES: compliant if done 75% or more of recommended level of EA and done 75% or more of recommended level of NMES usage
- EA + SET + NMES: compliant if done 75% or more of recommended level of EA, attended 50% or more SET sessions held by centre and done 75% or more of recommended level of NMES usage

These variables, excluding compliance classification, will be summarized at follow up time periods by treatment group using the ITT analysis set. Compliance classification will be summarised at the end of the intervention period. Summaries of continuous variables will be presented as mean and standard deviations if normally distributed, and as mean and inter-quartile ranges for skewed data. Categorical variables will be presented as frequencies and percentages.

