**Table 6 Summary of Protocol Deviation of randomised patients (ITT) by treatment**

Variables	Treatment  : NMES + EA and NMES+EA+SET N=(XX)	Control  : EA and EA+SET N=(XX)	Total N=(XX)
Protocol Deviation or Violation			
Protocol Deviation	XX (XX.X%)	XX (XX.X%)	XX (XX.X%)
Protocol Violation	XX (XX.X%)	XX (XX.X%)	XX (XX.X%)
Type of Protocol Deviation			
Device administration	XX (XX.X%)	XX (XX.X%)	XX (XX.X%)
Sampling	XX (XX.X%)	XX (XX.X%)	XX (XX.X%)
Visit outside window	XX (XX.X%)	XX (XX.X%)	XX (XX.X%)
Other, please give details	XX (XX.X%)	XX (XX.X%)	XX (XX.X%)
Other			
Break in SET classes	XX (XX.X%)	XX (XX.X%)	XX (XX.X%)
Classes did not commence within 2 weeks of randomisation	XX (XX.X%)	XX (XX.X%)	XX (XX.X%)
Device not in use	XX (XX.X%)	XX (XX.X%)	XX (XX.X%)
Height and Weight not recorded	XX (XX.X%)	XX (XX.X%)	XX (XX.X%)
Non-SET class patient (we are a SET centre)	XX (XX.X%)	XX (XX.X%)	XX (XX.X%)
Peripheral pulses not assessed	XX (XX.X%)	XX (XX.X%)	XX (XX.X%)
Received wrong treatment - patient bought own device	XX (XX.X%)	XX (XX.X%)	XX (XX.X%)
Problems with attendance to SEP class	XX (XX.X%)	XX (XX.X%)	XX (XX.X%)
Treadmill not increased as per protocol could only increase to a maximum of 7.5% and not 8%	XX (XX.X%)	XX (XX.X%)	XX (XX.X%)
Incomplete data measurement at baseline	XX (XX.X%)	XX (XX.X%)	XX (XX.X%)
Any Protocol Deviation or Violation by site			
Cambridge University Hospital	XX (XX.X%)	XX (XX.X%)	XX (XX.X%)
Dorset County Hospital	XX (XX.X%)	XX (XX.X%)	XX (XX.X%)
Hull and East Yorkshire Hospitals	XX (XX.X%)	XX (XX.X%)	XX (XX.X%)
Imperial College Healthcare	XX (XX.X%)	XX (XX.X%)	XX (XX.X%)
Newcastle Upon Tyne Hospitals	XX (XX.X%)	XX (XX.X%)	XX (XX.X%)
North Bristol	XX (XX.X%)	XX (XX.X%)	XX (XX.X%)
Nottingham University Hospitals	XX (XX.X%)	XX (XX.X%)	XX (XX.X%)
Royal Bournemouth & Christchurch Hospital	XX (XX.X%)	XX (XX.X%)	XX (XX.X%)
St George's University Hospitals	XX (XX.X%)	XX (XX.X%)	XX (XX.X%)
Taunton & Somerset	XX (XX.X%)	XX (XX.X%)	XX (XX.X%)
University Hospital Southampton	XX (XX.X%)	XX (XX.X%)	XX (XX.X%)

 Treatment: NMES + Local Available Exercise Therapy (NMES+EA and NMES+EA+SET) Control: Local Available Exercise Therapy (EA and EA+SET)

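### Control-arm use of the device is recorded only as an ad hoc deviation and does not enter the compliance, per-protocol or CACE definitions

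*Protocol*

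**What the plan says.** **Recording.** Protocol 5.6 (3-month visit) heads its item on device compliance and experience as applying to the device arm only. Within it: "Participants randomised to use the NMES device will be provided with a compliance diary to record device use details". The logger cross-check and the device questionnaire sit under the same item. The diary given to everyone covers SET attendance and asks participants to "record the type and frequency of exercise undertaken in their own time during the study period"; it has no item on device use. SAP 7.4 draws its compliance measures from the diaries.

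**Compliance rules.** SAP 7.2 judges each participant only against the treatments assigned. For controls at non-SET centres: "EA: compliant if done 75% or more of recommended level of EA". For controls in the SET stratum: "EA + SET: compliant if done 75% or more of recommended level of EA and attended 50% or more SET sessions held by centre". Neither rule requires that no device was used.

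**Analysis sets.** The per-protocol set in SAP 6.2 removes SET patients who attended no class and participants who withdrew early or withdrew their data. It does not remove controls who used a device.

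**Where switching appears.** SAP Table 6 has a deviation row, "Received wrong treatment - patient bought own device", with Treatment, Control and Total columns.

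**Compliance-adjusted analyses.** Protocol 8.3 promises causal-inference estimates that account for compliance with NMES, SET and EA, and Protocol 8.3.2 names a complier average causal effect (CACE) for the mechanistic outcomes. SAP 6.1 makes its CACE conditional on a difference in SET uptake. SAP 8.8.1 plans a subgroup analysis of compliers for the primary and secondary endpoints.

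**The concern.** Switching is plausible. SAP 5.6 states that the study is unblinded, Protocol 1.6 describes a home device that needs no clinician, and it adds: "The retail cost of the device is approximately £160". Patients already using such a device are excluded at entry, so the investigators regard prior exposure as relevant. After randomisation, when exposure would affect the contrast, controls are not asked about it.

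Two things are at stake. First, a control who used a bought device every day can count as a compliant control in SAP 8.8.1 and stay in the per-protocol set, so both analyses may compare device users with other device users. Second, a CACE for NMES needs device exposure in both arms, and the plan provides no systematic source for it in controls. The extent of switching, which a reader needs in order to interpret a small difference between arms, would be known only from whatever deviations happened to be filed.

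**Working it through.** **Inputs from the documents** (Protocol 8.1, SAP 5.7): difference 60 m, SD 120 m, two-sided 5% level, 90% power, 86 per group, 10% dropout, total 192. No allowance for switching is stated.

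**Reproducing the plan's figure.** The normal approximation gives 2 × (1.960 + 1.282)² × (120/60)² = 84.1, so 85 per group. The two-sample t calculation gives 86 per group, with power 90.3%. For dropout, 86/0.90 = 95.6, so 96 per group and 192 in total. The plan's figures reproduce.

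**Assumptions, not in the documents.** Let c be the share of controls who use a device and p the share of the device arm who use it. Every user gains 60 m, whichever arm they are in.

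- ITT difference = 60 × (p − c)
- CACE taking control use as zero = ITT / p = 60 × (1 − c/p)
- CACE using observed exposure in both arms = ITT / (p − c) = 60

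The first three result columns take p = 0.80; the next two vary p.

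| c | ITT, p = 0.80 | ITT / 0.80 | Understated by c/p | ITT / p at p = 1.0 | ITT / p at p = 0.75 |
|---|---|---|---|---|---|
| 2% | 46.8 m | 58.5 m | 2.5% | 58.8 m | 58.4 m |
| 5% | 45.0 m | 56.3 m | 6.3% | 57.0 m | 56.0 m |
| 10% | 42.0 m | 52.5 m | 12.5% | 54.0 m | 52.0 m |
| 20% | 36.0 m | 45.0 m | 25.0% | 48.0 m | 44.0 m |

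Check of the last formula at p = 0.80, c = 10%: 42.0/(0.80 − 0.10) = 60 m.

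**ITT power.** With 86 per group and full use in the device arm, power is 89.2%, 87.2%, 83.5% and 74.2% at c = 2%, 5%, 10% and 20%.

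**The SAP 8.8.1 compliers comparison.** That section points to SAP 8.9.6.4 for its definition. The tables there hold no rule, so the operative rule is the one in 7.2. If 10% of compliant controls used a device, dilution alone takes 60 m to 60 × 0.90 = 54 m. The two groups are also selected differently, because device-arm compliers must meet the NMES threshold as well. An assumed prognostic difference of +12 m or −12 m between the arms' compliers moves 54 m to 66 m or 42 m. Dilution acts downward, but the sign of the total bias cannot be determined.

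**The case against.** A reader might infer that switching is not measured at all. The documents do not support that. Table 6 counts bought devices by arm, Table 4 lists each deviation with treatment and start and end dates, and Protocol 9.6 sends all deviations through the CRF or eCRF to the chief investigator, with monthly reporting to quality assurance. What stands is narrower: a bought device is captured when it comes to light, without routine questioning or a measure of use, and no section carries it into an analysis definition.

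A reader might also infer that the compliance-adjusted effect is biased toward zero. That goes too far. No section specifies a CACE with control use set to zero: Protocol 8.3 and 8.3.2 leave exposure undefined, and the SAP's CACE is triggered by class attendance. For the compliers subgroup, selection can outweigh dilution in either direction. The attenuation formula therefore describes a choice that the plan leaves open.

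The size is also uncertain. The documents give no switching rate, and the 80% device-arm use is an assumption; the pilot in Protocol 1.5 reported 98.5% from diaries. Late buyers without the trial's familiarisation session may gain less than 60 m, which would reduce the attenuation.

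The Control column in Table 50 (device use) is weak evidence either way, because the same header is reused for SET and EA in Tables 49 and 51.

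None of this answers the central point: the stated rule classes an exposed control as compliant and ignores the exposure.

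**Conclusion.** The point holds as a gap in measurement and definition. Control device use has no systematic record and plays no part in the compliance, per-protocol or CACE definitions. The SAP 8.8.1 contrast is diluted to the extent that compliant controls used a working device, with the net bias undetermined. An NMES CACE is attenuated by the factor (1 − c/p) only if control use is taken as zero; at the assumed p = 0.80 the understatement runs from 2.5% at c = 2% to 25% at c = 20%. This assumes a beneficial effect that is the same for every user.

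The primary ITT analysis does not depend on these data. Switching would lower the size of its estimate and its power, but it remains a valid comparison of the two treatment policies. The sample size and ITT rules need no change.

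**What to change.** 1. At the 3-month visit, after the treadmill test, or by telephone if the visit is remote, ask every control whether they have used any NMES device since randomisation, with start date and frequency. Report the answers in the Control column of Table 50.
2. SAP 5.8 dates recruitment from March 2018 to a pause in March 2020, so many of these visits may already have passed. For those, use the recorded deviations and ask at the next follow-up contact.
3. In SAP 7.2, add to the EA and EA + SET definitions: and no NMES use in the treatment period.
4. State that any CACE for NMES uses observed device exposure in both arms.

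The cost is one question at an existing contact, one clause and one sentence. There are two downsides. The question could prompt a few controls to buy a device, but only after the primary endpoint has been measured. Controls asked late will recall less accurately. Item 3 corrects the misclassification but does not make SAP 8.8.1 a randomised comparison; it still conditions on behaviour after randomisation and should be reported as such.

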## 5.7 Summary of Visit Schedule

Imperial Clinical Trials Unit	NESIC Clinical Study Protocol V6.0 24/03/2020	Form Number CR001A-T
-------------------------------	---	-------------------------

Visit	Screening	Baseline*	Treatment Phase	Follow-up (months)†		
	1	2	0 to 3 months	3	4	5
Informed consent	X					
Pregnancy test 	X					
Ankle Brachial Pressure Index (ABPI) / positive stress test	X			X	X	X
Edinburgh Claudication Questionnaire	X					
Medical history	X					
Drug history	X			X	X	X
Peripheral pulse examination	X			X	X	X
Other exclusion criteria	X					
Randomisation		X				
Demography		X				
Vital signs		X				
EQ-5D-5L / SF-36 / ICQ		X		X	X	X
Treadmill test (ICD/ AWD)		X		X	X	X
Duplex Ultrasonography		X 		X 		
Laser Doppler Flowmetry		X 		X 	X	X
NMES training 		X				
SET booking 		X				
Compliance Diary (SET / device / EA)		X		X	X	X
Resource use diary		X	X	X	X	X
Weekly text messages			X			
Data logger		X	X			
Device experience questionnaire				X		
Safety reporting			X	X	X	X

\*baseline and screening visit occur on the same day if both the researcher and participant agree that informed consent has been adequately considered with time to ask questions

† These visits may take place remotely in the event that the participant is unable to attend in clinic or the site is unable to accommodate the on-site visit

women of child bearing potential a required to take a urine pregnancy test

At rest and during device use in device arm

NMES treatment groups only

SET centres only where applicable

## 6. TREATMENTS

### 6.1 Investigational Medical Device Details

This trial is being carried out under a MHRA Devices (Notice of No Objection). The device is therefore only to be used by the named investigators, for the participants specified in this protocol, and within the trial.

#### 6.1.1. Description of the Device

The Revitive IX System comprises of the following Components:

#### EMS Device: REVITIVE IX:

- C: Foot Pads
- D: LED Display Panel
- E: Time Setting Controls
- F: Foot pad Intensity Controls
- G: Electrode Pad Intensity Controls
- H: Power Button
- I: Location of Accessory and Power Sockets
- J: IsoRocker

Imperial Clinical Trials Unit	NESIC Clinical Study Protocol V6.0 24/03/2020	Form Number CR001A-T
-------------------------------	---	-------------------------

### AC Power Adaptor:

The AC/DC Power adaptor is a CE Marked Class II Portable AC Adaptor with a rated input of 100-240VAC, 50-60Hz, 0.18A and a Rated Output of 5.0VDC, Max 1.0A. The adaptor is certified to EN60601-1:2006 by TUV SUD Product Service GmbH. The AC adaptor is designed and manufactured in accordance with a Quality Management Systems certified to ISO 9001:2008.

### Remote Control:

The IR remote control is operated by 2 x 1.5v AAA batteries (supplied, not installed) and interacts with the digital display located on the main unit of Revitive Medic where the receiver is located. The remote control provides duplicate functions to the user interface on the Revitive Medic device. The Remote Control is designed and manufactured in accordance with a Quality Management System certified to ISO 9001:2015.

The Revitive IX system consists of an electrical muscle stimulation (EMS) device, AC/DC power adaptor and optional electrode pads. EMS is the application of electrical impulses that are of sufficient intensity to produce an artificial contraction of the muscle tissue. Revitive IX is indicated for electrical stimulation of the lower leg to:

- Reduce swelling in the legs/ankles/feet - caused by being immobile due to osteoarthritis or an injury
- Improve circulation to reduce or prevent blood-pooling (stasis) - caused by diabetes or by being immobile following surgery
- Reduce pain and discomfort in the legs/ankles/feet - caused by diabetic peripheral neuropathy or swelling (oedema) due to osteoarthritis or following surgery
- Increase muscle strength to help regain mobility in the legs affected by being immobile due to COPD, osteoarthritis or following surgery

Imperial Clinical Trials Unit	NESIC Clinical Study Protocol V6.0 24/03/2020	Form Number CR001A-T
-------------------------------	---	-------------------------

- Help maintain leg vein health - by increasing circulation, delivering more oxygenated-blood and reducing swelling (oedema) in the legs/feet/ankles.

In addition to the medical indications the Revitive family of devices are intended to provide electrical muscle stimulation for the following: Healthy individuals who have a sedentary lifestyle or spend long periods inactive, Revitive may help to:

- Reduce swollen feet and ankles
- Alleviate tired, aching & heavy legs, including cramp
- Improve circulation
- Help maintain leg vein health
- Increase muscle strength in the legs

The device is intended for home use for a recommended a minimum of 30 minutes treatment, up to a maximum of 3 hours treatment time per day as required. The device delivers electrical stimulation to the lower limb muscles through foot pads and/or through electrode pads which may be positioned on the lower limb.

The Revitive IX provides user control of intensity and duration of stimulation. It also has an additional IsoRocker feature that allows ankle movement during stimulation. When enabled, the IsoRocker allows Revitive IX to tilt back and forth as the muscles contract and relax. The user is able to choose whether to enable the IsoRocker feature on the device. Revitive IX also includes a remote control in addition to the controls on the device, and Revitive IX is reusable. It is supplied non-sterile with an AC adaptor, remote control (including 2 x 1.5v AAA batteries) and electrode pads as standard.

The technical characteristics of the Revitive IX device is summarised in the current version of the current version of the Investigator's Brochure.

